13.4. Reporting Adverse Events

The Investigator will notify the Sponsor of an adverse event by e-mail, facsimile, or telephone as soon as possible and no later than 24 hours from discovery for any serious /significant adverse events, and 2 days from discovery for any non-significant adverse event. In addition, a written report will be submitted by the Principal Investigator to the IEC/IRB according to their requirements (Section 13.4.2). The report will comment whether the adverse event was considered to be related to the test article, study treatment or study procedures.

13.4.1. Reporting Adverse Events to Sponsor

Serious/Significant Adverse Events

The Investigator will inform the sponsor of all serious/significant adverse events occurring during the study period as soon as possible by e-mail, fax, or telephone, but no later than 24 hours following discovery of the event. The Investigator is obligated to pursue and obtain information requested by the Sponsor in addition to that information reported on the eCRF. All subjects experiencing a serious/significant adverse event must be followed up and all outcomes must be reported.

When medically necessary, the Investigator may break the randomization code to determine the identity of the treatment that the subject received. The Sponsor and study monitor should be notified prior to unmasking the test articles.

In the event of a serious/significant adverse event, the Investigator must:

- Notify the Sponsor immediately
- Obtain and maintain in the subject's records all pertinent medical information and medical judgment for colleagues who assisted in the treatment and follow-up of the subject
- Provide the Sponsor with a complete case history which includes a statement as to whether the event was or was not related to the use of the test article
- Notify the IEC/IRB as required by the IEC/IRB reporting procedure according to national regulations

Unanticipated (Serious) Adverse Device Effect (UADE)

In the event of an Unanticipated (Serious) Adverse Device Effect (UADE), the Investigator will submit a report of the UADE to the Sponsor and IEC/IRB as soon as possible, but no later than 24 hours after the Investigator first learns of the effect. This report is in addition to the immediate notification mentioned above.

The Sponsor must conduct an evaluation of the UADE and must report the results of the evaluation to FDA, the IEC/IRB and participating Investigators within 10 working days after the Sponsor first receives notification of the effect.

Non-Serious Adverse Events

All non-serious adverse events, including non-serious adverse device effects, will be reported to the sponsor by the Investigator no later than 2 days from discovery.

13.4.2. Reporting Adverse Events to the Responsible IEC/IRB and Health Authorities

Adverse events that meet the IEC/IRB requirements for reporting must be reported within the IEC/IRB's written guidelines. Each clinical site will refer to and follow any guidelines set forth by their Approving IEC/IRB. Each clinical site will refer to and follow any guidelines set forth by their local governing Health Authorities.

The Sponsor will report applicable Adverse Events to the local health authorities according the written guidelines, including reporting timelines.

13.4.3. Event of Special Interest

None

13.5. Reporting of Pregnancy

Subjects reporting pregnancy (by self-report) during the study will be discontinued after the event is recorded as an Adverse Event. Once discontinued, pregnant participants and their fetuses will not be monitored for study related purposes. At the Investigator's discretion, the study participant may be followed by the Investigator through delivery. However, this data will not be collected as part of the clinical study database. Pregnant participants are not discontinued from device or solution related studies for safety concerns, but due to general concerns relating to pregnancy and device use. Specifically, pregnant women are discontinued due to fluctuations in refractive error and/or visual acuity that occur secondary to systemic hormonal changes, and not due to unforeseen health risks to the mother or fetus.

14. STATISTICAL METHODS

14.1. General Considerations

Statistical Analysis will be undertaken by the sponsor or under the authority of the sponsor. A general description of the statistical methods to be implemented in this clinical trial is outlined below.

All data summaries and statistical analyses will be performed using the SAS software Version 9.4 (SAS Institute, Cary, NC). Throughout the analysis of data, the results for each subject/eye will be used when available for summarization and statistical analysis. Unscheduled visits will be summarized separately and will be excluded from the statistical analysis.

Summary tables (descriptive statistics and/or frequency tables) will be provided for all baseline variables, efficacy variables and safety variables as appropriate. Continuous variables will be

summarized with descriptive statistics (n, mean, standard deviation (SD), median, minimum and maximum). Frequency count and percentage of subjects or eyes within each category will be provided for categorical data.

14.2. Sample Size Justification

Inner eyelid palpebral temperature has not previously been collected with the ICI-7320 infrared camera (Infrared Cameras Inc., Beaumont, TX) and a search of the peer reviewed literature failed to show published results with the device. Previous evaluations of inner eyelid temperature have focused primarily on the lower eyelid using infrared pyrometers. Given the lack of previous data, a formal sample size calculation cannot be completed. The sample size selected approaches the sample size required to meet the Central Limit Theorem and provide data for future sample size calculations.

14.3. Analysis Populations

Safety Population:

All subjects who were administered any test article excluding subjects who drop out prior to administering any test article. At least one observation should be recorded.

Intent-to-Treat (ITT) Population:

All randomized subjects regardless of actual treatment and subsequent withdrawal from study or deviation from protocol. At least one observation should be recorded.

Per-Protocol Population:

All subjects who have successfully completed all visits and did not substantially deviate from the protocol as determined by the trial cohort review committee prior to database hard lock (Per-Protocol Population). Justification of excluding subjects with protocol deviations in the per-protocol population set will be documented in a memo to file.

14.4. Level of Statistical Significance

All planned analysis for this study will be conducted with an overall type I error rate of 5%.

14.5. Primary Analysis

Eyelid Temperature will be analyzed using a linear or generalized linear mixed model depending on the distribution of temperatures. Treatment sequence, treatment, eyelid location (inner and outer) and the interaction between treatment and eyelid location will be included as fixed effects. Age and gender may also be included as covariates when necessary. Subject will be included as a random effect. An appropriate covariance structure will be used to model the residual errors between measurements within same subject across eyes (R-side). The covariance structure will be selected based on the finite-sample corrected Akaike's Information Criterion. Covariance structures considered include:

- Unstructured Covariance Structure (UN)
- Homogenous Compound symmetry (CS)

Comparisons between the two treatments will be carried out using two-sided 95% confidence intervals constructed for least-square mean differences (MiBo ThermoFlo minus Bruder mask).

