Study Responsible Clinician	<hr/> 
See Electronic Signature Report [name], OD Principal Research Optometrist
	<hr/> 
DATE

Clinical Operations Manager	<hr/> 
See Electronic Signature Report [REDACTED] Clinical Operations Department
	<hr/> 
DATE

Biostatistician	<hr/> 
See Electronic Signature Report [REDACTED] Biostatistician II, Clinical Sciences
	<hr/> 
DATE

Biostatistics Reviewer	<hr/> 
See Electronic Signature Report [REDACTED]. Senior Manager of Biostatistics, Clinical Sciences
	<hr/> 
DATE

Data Management	<hr/> 
See Electronic Signature Report [REDACTED] Clinical Project Manager – Data & Systems, Clinical Operations
	<hr/> 
DATE

Approver:	<hr/> 
See Electronic Signature Report [REDACTED] Director of Global Medical Affairs
	<hr/> 
DATE

CHANGE HISTORY

Version	Originator	Description of Change(s) and Section Number(s) Affected	Date
1.0	[name] & [name]	Original Protocol	01 OCT 2018
2.0	[name]	
Clarification for treatment of Bruder MaskUpdate to Section 2.2Topography added to Table 3	15 NOV 2018

[figure not shown]
SYNOPSIS

Protocol Title	MiBo ThermoFlo Lid Temperature Evaluation
Sponsor	JJVC, [name]
Clinical Phase	Phase 4
Trial Registration	This study will be registered on ClinicalTrials.gov by the Sponsor
Test Article(s)	Investigational Product: MiBo ThermoFlo Control Product: Bruder Moist Heat Single Eye Compress
Wear and Replacement Schedules	N/A
Objectives	
Determine anterior and posterior eyelid temperature after use of the MiBo ThermoFlo following standard clinical protocol and evaluate changes to the tear film with one MiBo ThermoFlo treatment session.
 
Primary Objective: Determine the temperature of the palpebral conjunctiva after MiBo ThermoFlo treatment and Bruder Mask (i.e. hot compress) treatment using the ICI-7320 infrared camera (Infrared Cameras Inc., Beaumont, TX)
 
Secondary Objectives: Tear Film Lipid Layer Thickness and Non-Invasive Tear Break Up Time post treatment

Study Endpoints	
Primary endpoint(s): Palpebral Conjunctival Temperature
 
Secondary endpoint(s): Tear Film Lipid Layer Thickness, Non-invasive tear break up time (NITBUT)

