2.3. Hypotheses

1. After 12 minutes of treatment, the MiBo ThermoFlo will not heat the posterior eyelid palpebral conjunctiva to a temperature of 40°C.

Background: Ocular surface temperature is usually 34.03 ± 0.51 °C in the ‘normal’ eye. The temperature required to melt obstructive secretions in the Meibomian glands ranges from 32-45°C but the more severely obstructed glands present in MGD would require a temperature of >40°C, for effective treatment. There is an approximate 5°C difference in temperature between heat applied on the external eyelid surfaces and that which reaches the inner surface of the lids (palpebral conjunctiva), where the meibomian glands are located. This difference is due to both dissipation of heat while passing through the lid tissues and to constant movement of blood through vasculature wicking heat away from the lids. Therefore, achieving the desired temperature of 40°C at the palpebral conjunctiva requires a constant heat of at least 45°C be maintained on the outer lid surface, a temperature which may be both uncomfortable and risk causing thermal injury to the eyelid skin.

Other Observations

1. After 10 minutes of treatment, the Bruder Mask will not heat the posterior eyelid palpebral conjunctiva to a temperature of greater than 40°C.
2. There is no difference in posterior eyelid palpebral conjunctiva between the Bruder Mask and the MiBo ThermoFlo

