4. STUDY DESIGN AND RATIONALE

4.1. Description of Study Design

This study is a prospective, contralateral, single-site, single-visit unmasked evaluation of external and internal eyelid temperature after treatment with the MiBo ThermoFlo. Approximately 20 subjects will be evaluated for enrollment in the study, with a goal of a minimum of 12 subjects completed. If a subject meets all eligibility criteria then the subject will be randomly assigned to 1 of 2 treatment sequences in a contralateral fashion, (1) MiBo ThermoFlo (left eye) / Bruder mask (right eye) or (2) Bruder mask (left eye) / MiBo ThermoFLo (right eye). Subjects will undergo each treatment for a period of 12 minutes for the MiBo ThermoFlo and 10 Minutes for the Bruder mask, per the manufacturer recommendations.

The study visit is expected to last approximately 2.5 hours. Subjects will undergo Meibography, tear lipid layer measurements, non-invasive tear break-up time, eyelid photography and the study treatments (MiBo ThermoFlo and Bruder mask).

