1.8	Eligibility after Baseline	All responses to Inclusion Criteria questions must be answered “yes” and all responses to Exclusion Criteria questions must be answered “no” for the subject to be considered eligible.	

Visit 1: Baseline			
Step	Procedure	Details	
		If subject is deemed to be ineligible after baseline, proceed to Final Evaluation and complete all forms.	

Visit 1: Treatment			
Step	Procedure	Details	
1.9	Eyelid Photography	The upper and lower eyelid margins of the subject will be photographed, OD, OS	Work Aid: Eyelid Photography
1.10	Tear Lipid Layer Thickness (LLT)	Measure the pre-treatment tear film LLT using the TearScience Lipiview, (OD, OS)	Work Aid: TearScience LipiView II Lipid Layer Thickness Measurement
1.11	Non-Invasive Tear Break Up Time (NITBUT)	Perform pre-treatment NITBUT using Oculus Keratograph 5 (OD, OS)	SOP_C12_Oculus Keratograph_V2
1.12	Corneal Topography	Perform pre-treatment corneal topography with the Oculus Keratograph	SOP_C12_Oculus Keratograph_V2
1.13	Thermography	Perform pre-treatment measurement of the external eyelid and palpebral conjunctival temperature for the upper and lower lids, (OD and OS)	SOP_C31_Thermography_V1.0
1.14	Randomization	Randomize treatment to eye using the randomization schedule	
1.15	MiBo ThermoFlo	Perform 12-minute MiBo ThermoFlo treatment on the eye indicated on the randomization schedule using the ThermoFlo Elite Eye Pad.	Work Aid: MiboFlo
1.16	Thermography	Immediately perform post-treatment measurement of the external eyelid and palpebral conjunctival temperature for the upper and lower lids, collecting data for the lower lid first.	SOP_C31_Thermography_V1.0
1.17	Bruder Mask	Heat the Bruder Mask per the manufacturer's instructions, measure the mask surface temperature and perform 10 minute Bruder Mask treatment on the contralateral eye.	Work Aid: Bruder Mask_V2

Visit 1: Treatment			
Step	Procedure	Details	
		Note: The Bruder Mask should be placed gently on the closed eyelids. Do not apply pressure on the mask and eye.	
1.18	Thermography	Perform post-treatment measurement of the external eyelid and palpebral conjunctival temperature for the upper and lower lids	SOP_C31_Thermography_V1.0
1.19	Tear Lipid Layer Thickness (LLT)	Measure the post-treatment tear film LLT using the TearScience Lipiview, OD, OS	Work Aid: TearScience LipiView II Lipid Layer Thickness Measurement

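### Pre-treatment lid temperature is measured in both eyes before randomisation, but the Section 14.5 model does not use it to sharpen the MiBo minus Bruder comparison

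*Combined protocol and SAP*

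**What the plan says.** The schedule in Section 7.2 requires at step 1.13: "Perform pre-treatment measurement of the external eyelid and palpebral conjunctival temperature for the upper and lower lids, (OD and OS". Step 1.14 follows: "Randomize treatment to eye using the randomization schedule". A baseline on the outcome's own scale, surface and instrument therefore exists for each eye before allocation.

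The model in Section 14.5 has these fixed effects: "Treatment sequence, treatment, eyelid location (inner and outer) and the interaction between treatment and eyelid location will be included as fixed effects". Subject is a random effect. The only other covariates named are optional: "Age and gender may also be included as covariates when necessary". The planned inference is: "Comparisons between the two treatments will be carried out using two-sided 95% confidence intervals constructed for least-square mean differences (MiBo ThermoFlo minus Bruder mask". Sections 14.6 and 14.7 plan no further analyses, and Section 14.1 provides only descriptive summaries of baseline variables.

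Section 14.5 calls the response eyelid temperature without saying before or after treatment. That the post-treatment reading is meant has to be inferred from elsewhere, for example the primary objective in the Synopsis: "Determine the temperature of the palpebral conjunctiva after MiBo ThermoFlo treatment and Bruder Mask (i.e. hot compress) treatment".

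On size, Section 4.1 says: "Approximately 20 subjects will be evaluated for enrollment in the study, with a goal of a minimum of 12 subjects completed". Section 14.2 states that no formal sample size calculation could be done.

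**The concern.** The treatment contrast compares two eyes of one person. Whatever the eyes share cancels. What does not cancel is any difference between them that was there before treatment. If the eyes that happen to be allocated to MiBo start slightly warmer, part of that head start is counted as treatment effect. The data needed to remove it are collected and then left out of every planned inferential analysis.

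The point bears on the second of the other observations in Section 2.3: "There is no difference in posterior eyelid palpebral conjunctiva between the Bruder Mask and the MiBo ThermoFlo". The interval for that contrast is the only comparison that 14.5 plans, and it rests on 12 to 20 subjects. It may be wider than it needs to be, and it would mislead most in a trial with a large chance imbalance. If the choice is left until the data are in, adjusting or not adjusting becomes a data-dependent decision.

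**Working it through.** The plan has no figure of its own to reproduce, so the calculation reduces the model to one MiBo minus Bruder difference per subject at one lid surface.

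**Inputs**
- n = 12 (minimum completing) and n = 20 (target), Sections 4.1 and 4.3.
- Two-sided 95% interval, Section 14.5.
- r, the correlation between a subject's between-eye difference before treatment (B) and after treatment (D). It is not in the documents; assumed 0 to 0.7.
- The only temperature spread given is 0.51°C, for the ocular surface of a normal eye (Section 2.3). No lid SD is given.

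**1. What the planned model removes.** The random subject effect cancels the baseline level common to both eyes. In a simulation with 12 subjects, the mean of D had a correlation of about 0 with the subject-level baseline, but 0.49 with the between-eye baseline imbalance. Age and gender are the same for both eyes, so as main effects they cannot remove it either.

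**2. Expected interval width.** The unadjusted analysis is the mean of D with n-1 degrees of freedom. The adjusted analysis is the intercept from regressing D on B, with n-2. The ratio of widths, adjusted to unadjusted, is

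sqrt[(1 - r²)(n-2)/(n-3)] × t(0.975, n-2)/t(0.975, n-1).

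For n = 12 and r = 0.5: sqrt(0.75 × 10/9) × 2.228/2.201 = 0.913 × 1.012 = 0.924.

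| r | n = 12 | n = 20 |
|---|---|---|
| 0 | 1.067 | 1.033 |
| 0.3 | 1.018 | 0.985 |
| 0.5 | 0.924 | 0.894 |
| 0.7 | 0.762 | 0.738 |

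Setting the ratio to 1 gives a break-even r of 0.349 (n = 12) and 0.250 (n = 20).

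**3. Effect of a chance imbalance.** In simulation at n = 12, if the MiBo eyes start 1 standard error warmer, the unadjusted estimate shifts by about 0.48 of its own standard error at r = 0.5 and 0.68 at r = 0.7. The adjusted estimate shifts by about 0.

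**4. Coverage.** With 200,000 simulated trials per case (bivariate normal), both analyses cover 95% overall. In the 10% of trials where the standardised mean of B exceeds 1.645 in absolute value:

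| r | Unadjusted, n = 12 | Unadjusted, n = 20 | Adjusted, both |
|---|---|---|---|
| 0.3 | 92.0% | 91.7% | about 95% |
| 0.5 | 86.9% | 86.4% | about 95% |
| 0.7 | 78.9% | 77.6% | about 95% |

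**5. Size in degrees.** The 95% range of the mean imbalance is ±1.96 × 0.51 × sqrt[2(1-ρ)]/sqrt(n), where ρ is an assumed correlation between a subject's two eyes. With ρ from 0.5 to 0.95 this is ±0.29 to ±0.09°C at n = 12 and ±0.22 to ±0.07°C at n = 20.

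**The case against.** The planned analysis is valid. Eyes are randomised within subject, the shared level cancels, and allocation in blocks of 2 should nearly balance which eye receives MiBo, so a systematic right-left difference largely drops out. What remains is a choice between two unbiased analyses, and the gain depends on an r that nobody has measured. At n = 12 adjustment widens the expected interval for any r below about 0.35; in simulation the adjusted interval was the wider one in 81%, 63% and 36% of trials at r = 0, 0.3 and 0.5. There is a reason to expect a lower r: the Bruder eye's baseline is taken before the whole MiBo session and its thermography (steps 1.15 and 1.16). The poor coverage applies to a selected tenth of trials; the other nine tenths over-cover (95.3%, 95.9% and 96.9% at n = 12 for r = 0.3, 0.5 and 0.7). The imbalance is a fraction of a degree, the study is a pilot, and the contrast is not its main hypothesis. A baseline term also has a price under the no-imputation rule of Section 14.9: a missing baseline reading takes post-treatment readings out of the adjusted model.

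All of this stands as a limit on the size of the gain, and the missing-data point needs a sentence in the plan. None of it supplies a use for the baseline or settles the choice in advance. The payoff is uneven: at worst about 7% or 3% extra width, against 24% to 26% less at r = 0.7. An unknown r is a reason to fix the analysis now.

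**Conclusion.** The concern holds, as an avoidable inefficiency and not as a bias or an inflated error rate. The baseline is measured in both eyes before randomisation and is absent from the 14.5 model, and no other planned inferential analysis uses it. Adjustment pays if r exceeds about 0.35 with 12 subjects or 0.25 with 20, and costs a little below that. The width figures assume one paired difference per subject and one slope; the coverage figures also assume bivariate normal differences. The range in degrees borrows an ocular-surface SD for the lid. The conclusion concerns only the MiBo minus Bruder contrast. The main hypothesis in Section 2.3, about reaching 40°C, is an absolute post-treatment temperature and is not touched. The change is worth making before the data are seen; confidence that it will narrow the interval is moderate because r is unknown.

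**What to change.** In Section 14.5:

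- State that the response is the post-treatment temperature.
- Pre-specify the matching pre-treatment reading (same eye and surface, and same lid if lids are modelled separately) as a covariate. Enter it as two terms: the subject's mean over both eyes for that surface, and the eye's deviation from that mean. Only between-eye differences then inform the treatment contrast.
- Say whether the baseline slope is common to the inner and outer surfaces or separate. The figures above correspond to a slope fitted for one surface on its own.
- Report the unadjusted contrast beside it as a sensitivity analysis, using all available post-treatment readings, and say how a missing baseline is handled.

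The optional age and gender wording can stay.

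The cost is a few sentences and no new measurements. The statistical downside is an interval about 7% (n = 12) or 3% (n = 20) wider if r is near 0, plus any readings lost from the adjusted model through a missing baseline. Reporting r and the residual SD from the adjusted model would also serve the aim in Section 14.2 of informing later sample sizes.

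### Section 14.5 adjusts for treatment sequence, which drops out of the MiBo minus Bruder contrast when pairs are complete, and omits eye (OD/OS), the design factor that can widen its interval

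*Combined protocol and SAP*

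**What the plan says.** Section 4.1 has each eligible subject "randomly assigned to 1 of 2 treatment sequences in a contralateral fashion", and defines the two options as ("1) MiBo ThermoFlo (left eye) / Bruder mask (right eye) or (2) Bruder mask (left eye) / MiBo ThermoFLo (right eye"). The sequence label therefore records which eye gets which device. It does not record time order.

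Section 14.5 gives the mean model: "Treatment sequence, treatment, eyelid location (inner and outer) and the interaction between treatment and eyelid location will be included as fixed effects". The optional covariates are both between-subject: "Age and gender may also be included as covariates when necessary". It adds: "Subject will be included as a random effect". Eyes are mentioned only in the residual covariance: "An appropriate covariance structure will be used to model the residual errors between measurements within same subject across eyes (R-side". The reported comparison uses "two-sided 95% confidence intervals constructed for least-square mean differences (MiBo ThermoFlo minus Bruder mask", and Section 14.4 sets an "overall type I error rate of 5" percent. No section adds an OD/OS term to the mean.

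**The concern.** The model statement reads as if carried over from a crossover, where sequence and period are the usual design terms. Here the counterpart of period is eye, because each subject gives one measurement set per eye and randomization decides which device goes on which eye. The model keeps the between-subject label, which the paired contrast already cancels, and leaves out the within-subject factor.

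Any systematic right/left difference in measured temperature is then treated as noise. The MiBo minus Bruder interval is wider than the design requires. If the completers are not split evenly between the two assignments, the estimate also shifts. This interval is the only comparison Section 14.5 specifies, it rests on 12 to 20 subjects, and Section 14.2 makes no precision calculation that could absorb the loss.

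**Working it through.** The plan states no power, effect size or right/left difference, so there is no figure of its own to reproduce. The check is algebra followed by numbers.

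**Inputs from the documents.** Model terms (14.5); meaning of sequence (4.1); blocks of 2 (5.1); 20 subjects targeted and at least 12 completing (4.3); no imputation (14.9); a temperature SD of 0.51 °C for the untreated ocular surface (2.3), used only as a proxy.

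**Assumed.** The right/left offset delta, and the between-eye correlation rho.

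**Step 1: what cancels.** Let d be one subject's MiBo minus Bruder difference, tau the device effect, and delta the OD minus OS difference under the same treatment. Then d = tau + delta if MiBo is on the right eye, and d = tau − delta if it is on the left. The full offset enters with coefficient ±1. A sequence effect adds the same amount to both eyes, so it cancels from d.

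Mixed-model fits on simulated complete pairs agree. At 8/4 with a 5 °C sequence effect built in, the estimate was 0.73362 (SE 0.13663) both with and without sequence. With delta = 0.5 °C, adding eye at 6/6 left the estimate alone and cut the SE from 0.169 to 0.095.

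**Step 2: interval width, written for the paired palpebral difference.** Let m = (n_OD − n_OS)/N, where n_OD and n_OS count completers with MiBo on the right or left eye.

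- Without eye: half-width = t(N−1) × √{[sd_d² + delta²(1 − m²)N/(N−1)]/N}
- With eye: half-width = t(N−2) × sd_d × ½√(1/n_OD + 1/n_OS)

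At 6/6, t(11) = 2.201 and t(10) = 2.228, and both SEs carry the factor 1/√12. The ratio is therefore (2.201/2.228) × √(1 + delta² × 12/11), with delta in units of sd_d. The last two columns are averages of simulated half-widths (40,000 runs per cell), so they differ slightly from the formula.

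| delta (SD) | formula, 6/6 | simulated, 6/6 | simulated, 10/10 |
|---|---|---|---|
| 0 | 0.99 | 0.99 | 0.997 |
| 0.25 | 1.02 | 1.024 | 1.03 |
| 0.5 | 1.11 | 1.119 | 1.122 |
| 1 | 1.43 | 1.440 | 1.433 |

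Completing all 20 does not remove the loss.

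**Step 3: the same in °C, by proxy.** With rho = 0.5, sd_d = 0.51 × √(2 × 0.5) = 0.51 °C. At 6/6 the half-width with eye is 2.228 × 0.51/√12 = 0.328 °C. Without eye and with delta = 0.3 °C it is 2.201 × √[(0.2601 + 0.09 × 12/11)/12] = 0.380 °C; with delta = 0.5 °C it is 0.464 °C. Across rho 0.3 to 0.8, the ratio of the variance of d without eye to that with eye runs from 1.27 to 1.94 (0.3 °C) and from 1.75 to 3.62 (0.5 °C).

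**Step 4: bias.** Without eye, bias = delta × m.

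- 6/6: 0
- 7/5, 0.3 °C: 0.3 × 2/12 = 0.05 °C
- 8/4, 0.3 °C: 0.3 × 4/12 = 0.10 °C
- 11/9, 0.3 °C: 0.3 × 2/20 = 0.03 °C

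With eye the bias is 0 in each case.

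**Step 5: error rate.** Simulated rejection under no device difference, without eye, was 2.6% (0.3 °C) and 0.7% (0.5 °C) at 6/6, and 5.6% and 5.1% at 8/4. With eye it stayed near 5% throughout.

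**Step 6: cost if delta is 0.** At 6/6, 2.228/2.201 = 1.012, about 1%. At 10/10 it is about 0.3%. At 8/4, ½√(1/8 + 1/4) = 0.306 against 1/√12 = 0.289, and 0.306/0.289 × 1.012 gives about 7%. Eye narrows the expected interval once delta exceeds about 0.15 SD (N = 12) or 0.08 SD (N = 20).

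**The case against.** The best defence is that this is a small efficiency matter in a pilot. The documents report no right/left temperature difference, and the thermography SOP repeats the same steps on the fellow eye. At delta 0.25 the gain is only 2%. Balanced completion gives no bias and a conservative interval. Section 2.3 lists the device comparison under other observations; its numbered hypothesis concerns MiBo against 40 °C. All of this stands, and it limits the size of the point.

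A reader might go further and infer that the contrast is biased or that its type I error exceeds 5%. The documents do not support that. Blocks of 2 hold the imbalance at randomization to one subject. Randomization (step 1.14) follows the eligibility check (step 1.8), and what remains is part of a single visit of about 2.5 hours. Even if 20 were randomized and 8 were then lost at random, a split of exactly 8/4 in either direction has probability 2 × C(10,8) × C(10,4)/C(20,12) = 2 × 45 × 210/125,970, about 15%. Any bias is probably a few hundredths of a degree.

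Nor is sequence useless in every case. The ITT population admits incomplete data, and with 2 of 12 Bruder eyes missing in a simulated set, sequence moved the estimate from 0.622 to 0.615. That is a reason to add eye without deleting sequence.

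What the defence does not supply is a reason to leave eye out. The trial randomizes by eye, and Section 2.3 expects no difference between devices, so an unnecessarily wide interval leans toward that expectation.

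**Conclusion.** The point holds as a cheap improvement to the model and not as a threat to validity. With complete pairs, sequence does nothing for the contrast, and eye is the missing design factor. The likely harm is a conservative interval, with the loss depending wholly on an assumed offset: none at delta 0, about 12% at 0.5 SD and 44% at 1 SD for 6/6. The °C figures also rest on 0.51 °C as a proxy SD and on rho.

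Two limits apply. An eye term does not address order, because steps 1.15 to 1.18 in Section 7.2 place MiBo before Bruder for every subject. It also does not test the 40 °C hypothesis.

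**What to change.** In Section 14.5, add eye (OD/OS) as a fixed effect, preferably with eye × eyelid location. Keep sequence; it does no harm.

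The interaction matters for the palpebral contrast. With complete pairs it makes that contrast equal to the equal-weighted average of the two sequence means, which is also the intercept from regressing each subject's palpebral difference on a ±1 assignment code. An eye main effect alone assumes the same offset on the inner and outer lid and pools the two. In one simulated 8/4 data set with a 0.6 °C offset and a true difference of 0, the planned model gave 0.164, eye alone −0.037, and the equal-weighted average −0.003.

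The cost is one within-subject degree of freedom per eye term, with the interval widths given in step 6 of the working.

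First reconcile Section 5.1 with Section 4.1. As written, Section 5.1 lists the same allocation twice, with MiBo on the left eye and Bruder on the right in both. Read literally, eye would be fully confounded with treatment and no eye term could be estimated.
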